4.7.1 Data collection for nurse survey

For the nurse survey, the research team will collect nurse name. Nurse name will be collected and nurse responses will be merged into the administrative datasets. The identifying information will be kept separate from the survey responses. A unique code, not containing any identifying information, will be used to analyze nurses' responses.

The Evaluation team has executed data use agreements with the following agencies:

- **BAA with Nurse Family Partnership, for implementation data.** These data will be used to describe the implementation of Nurse Family Partnership in South Carolina during the study period, its adherence to program fidelity standards, the dosage received by treatment group participants and the exposure of control group members to NFP services.
- **BAA with South Carolina Department of Health and Human Services, for individually identified health data.** These data will be used to measure the effects of NFP on maternal and child health outcomes.
- **BAA with South Carolina Revenue and Fiscal Affairs Office, for individually identified health data.** These data will be used to measure the effects of NFP on maternal and child health outcomes.
- **DUA with South Carolina Revenue and Fiscal Affairs Office, for Public Use Encounter Data.** These data include encounter level Inpatient, Outpatient Surgery, Emergency Department, and Imaging records from 2010-2014. Analysis will focus on women with at least one childbirth (from diagnosis and procedure codes) whose primary payer is Medicaid and children whose primary payer is Medicaid, but records for other individuals will be used to conduct comparison analyses. These data will be used to design the analysis plan for this study.
- **DUA with South Carolina Revenue and Fiscal Affairs Office, for Encounter Data with Restricted Elements.** Records (any inpatient, outpatient surgery, emergency department discharge records or imaging records) will be matched to a master list of study subjects using First Name, Middle Name, Last Name, Social Security Number, and Date of Birth. These data will be used to measure the effects of NFP on child injury.
- **DUA with South Carolina Department of Health and Environmental Control, for historical birth certificate data.** Historical Vital Statistics data will aid the understanding of the study population. Our research team will use the data to conduct power calculations for various outcomes, to explore the predictive strength of potential control variables, and to understand determinants of maternal and child health in the Medicaid population. These data will be used to design the analysis plan for this study.
- **DUA with South Carolina Department of Health and Environmental Control, for matched birth certificate data, including child's name and date of birth.** These data will be used to measure the impact of NFP on pre-term birth and birth spacing for study participants.
- **DUA with The University of South Carolina, for matched data on MIECHV-funded home visiting programs.** These data will be used to assess the proportion of study participants who receive other home-visiting services funded by the Maternal, Infant, and Early Childhood Home Visiting (MIECHV) program.
- **DUA with First Steps, for matched data on study participants' participation in home-visiting programs affiliated with First Steps.** These data will be used to assess the proportion of study participants who receive other home-visiting services.

- **DUA with South Carolina State Law Enforcement Division, for matched data on arrests, custody, offense, and judicial outcomes.** Records will be matched to a master list of study subjects using First Name, Middle Name, Last Name, Social Security Number, and Date of Birth. These data will be used to measure the effects of NFP on criminal behavior.
- **DUA with South Carolina State Law Enforcement Division, for historical and current de-identified data for the entire state of South Carolina on arrests, custody, offense, and judicial outcomes.** These data will be used to improve our understanding of the study population. It will be used to conduct power calculations for various outcomes, to explore the predictive strength of potential control variables, and to understand determinants of maternal and child mental health.
- **DUA with South Carolina Department of Mental Health, for matched data on mental health diagnoses and services.** Records will be matched to a master list of study subjects using First Name, Middle Name, Last Name, Social Security Number, and Date of Birth. These data will be used to measure the effects of NFP on mental health.
- **DUA with South Carolina Department of Mental Health, for historical and current de-identified data on mental health diagnoses and services.** These data will be used to improve our understanding of the study population. It will be used to conduct power calculations for various outcomes, to explore the predictive strength of potential control variables, and to understand determinants of maternal and child health.
- **DUA with South Carolina Department of Education, for matched data on test scores, enrollment, attendance, and disciplinary action.** Records will be matched to a master list of study subjects using First Name, Middle Name, Last Name, Social Security Number, and Date of Birth. These data will be used to measure the effects of NFP on education.
- **DUA with South Carolina Department of Education, for historical and current de-identified data on test scores, enrollment, attendance, and disciplinary action.** These data will be used to improve our understanding of the study population. It will be used to conduct power calculation for various outcomes, to explore the predictive strength of potential control variables, and to understand determinants of maternal and child health.
- **DUA with South Carolina Department of Corrections, for matched data on incarceration.** Records will be matched to a master list of study subjects using First Name, Middle Name, Last Name, Social Security Number, and Date of Birth. These data will be used to measure the effects of NFP on incarceration.
- **DUA with South Carolina Department of Corrections, for historical and current de-identified data on incarceration.** These data will be used to improve our understanding of the study population. It will be used to conduct power calculation for various outcomes, to explore the predictive strength of potential control variables, and to understand determinants of maternal and child health.
- **DUA with South Carolina Department of Social Services, for matched data on the use of social services and human services.** Records will be matched to a master list of study subjects using First Name, Middle Name, Last Name, Social Security Number, Date of Birth, and Medicaid number. These data will be used to measure the effects of NFP on use of social services and human services.
- **DUA with South Carolina Department of Social Services, for historical and current de-identified data on the use of social services and human services.** These data will be used to improve our understanding of the study population. It will be used to conduct power calculation for various outcomes, to explore the predictive strength of potential control variables, and to understand determinants of maternal and child health.

4.8. Is there a data and safety monitoring plan (required for greater than minimal risk studies)?
 No Yes: If yes; describe the plan

4.9. Are there any anticipated circumstances under which participants will be withdrawn from the research without their consent?
 No Yes: If yes; describe the circumstances as well any associated procedures to ensure orderly termination

5. Data/Statistical Analyses Plan

5.1. Briefly describe the plan for data analysis (including the statistical method if applicable)

To answer the research questions, we will use an instrumental variable (IV) approach and administrative data to estimate the local average treatment effect of NFP on intervention group members who actually participate in NFP relative to the services consumed by the control group. This estimated effect of NFP is of policy interest because it represents the impact of NFP on those moms who are likely to participate in NFP were the program to expand and offer additional program slots through a lottery. The source of non-compliance that it explicitly captures is that some mothers randomized into the intervention group may never receive NFP services (i.e. the “enrollment rate” is less than 1). According to the enrollment protocol, no mothers in the control group should be enrolled in NFP services. To the extent that some sample members in the control group receive services from similar home visiting programs that may also affect outcomes, this model estimates the effect of NFP relative to the mix of other home-visiting programs that the control group receives, rather than relative to no home-visiting service at all.

The impact estimate is the regression-adjusted difference between the average outcomes of treatment group participants and control group participants. Impact estimates with p-values less than 0.05 (two-tailed test) will be considered statistically significant and provide evidence that there are likely true differences between the groups as a result of NFP.

In addition to these impact estimates, we will also report the percentage of treatment group participants who reported living in a low-income zip code (LIZC) at the time of study enrollment. (LIZC is defined as a zip code in which fifteen percent (15%) or more of households have incomes below the federal poverty guidelines according to 2012 Census Bureau Data.) Before reporting this percentage, we will use Google Map’s Application Programming Interface (API) to confirm that the participant’s self-reported zip code corresponds with their self-reported street address. To do this, we will send a file of unformatted, raw street addresses, cities, and states to Google’s API to return formatted addresses, including zip code. We will then compare these formatted zip codes to the zip codes reported by each study participant. The file we send to Google Map’s API will include a greater number of ‘fake’ (i.e. non-study participant) addresses than actual addresses, to maintain study participants’ confidentiality.

We will also analyze how the main impact estimates vary within our sample. In particular some mothers and their children may be at higher risk for adverse outcomes such as preterm birth or childhood injury. We will define “risk” based on poverty rate in the census tract in which a mother is enrolled. In order to perform this analysis, we will match participants’ self-reported addresses to census tracts in two ways. First, we will send a de-identified file that will only include a randomly generated ID number and the following address information of unformatted, raw street addresses, cities, states, and zip codes to the United States Census Bureau’s Geocoder tool as well as to the geocoding service, Geocodio. We will match addresses to census tracts using both the Census Bureau Geocoder tool as well as Geocodio in order to be able to cross validate the accuracy of the census tract mapping. Mapping to the wrong census tract or failing to map to a census tract will reduce the accuracy of our analysis. The randomly generated ID number will allow for linking census tract

information back to our data. Second we will check perform a last check of the accuracy of our first method of linking to census tracts by retrieving the latitude and longitude of participants' addresses via the Google Maps API in the same procedure described above. We will then use these latitude and longitude coordinates to link addresses to census tracts using cartographic boundary files provided by the Census Bureau. Once we have matched participants' addresses to census tracts, we will investigate how our main impacts vary by the census tract rate of poverty. The files we send to The Census Bureau's Geocoder tool, to Geocodio, and to Google Map's API will include a greater number of 'fake' (i.e. non-study participant) addresses than actual addresses, to maintain study participants' confidentiality.

5.2. Is there a sample size/power calculation?

Yes: If yes; describe the calculation and the scientific rationale, and, if applicable, by site and key characteristics such as participant demographics

NFP plans to serve 4,000 families in South Carolina between January 2016 and January 2020. Our power analysis suggests that with 4,000 families served in the treatment group, we will need a 2:1 T:C ratio (or 2,000 control group families) to achieve 80% or higher chance of detecting statistically significant effects on two out of the three primary outcomes (pre-term birth, birth spacing, and childhood injury), if the true effect size of the outcomes equals the expected effect size provided by NFP. These expected effect sizes are based on analysis of previous NFP trials and baseline knowledge on the current population of South Carolina's Medicaid-eligible first-time mothers and the assumptions summarized below.

As of May, 2015, the expected effective sizes, in percentage difference between the treatment group and the control groups, is -20% for the measure of pre-term birth, -18% for the measure of birth spacing, and -13% for the measure of child injury. In addition, we need 95% or more of women randomized into the treatment group to receive NFP services, and at most 5% of the control group that receives a home visiting program that has as much impact as NFP. Furthermore, our power calculation is based on the assumption that the distribution of the outcomes variables have the following mean (standard deviation) combinations in the absence of NFP intervention: 0.12 (0.32) for the binary measure for pre-term birth, 0.14 (0.34) for the binary measure of birth spacing, and 0.18 (0.30) for the measure of child injury.

With this set of assumptions, we need to enroll at least 6,000 women into the evaluation with a 2:1 treatment to control ratio to achieve near 80% or higher power. With these numbers we will have roughly 70% power to detect a statistically significant effect on the birth-spacing measure if the true effect size is -18%. We will have a nearly 100% chance to detect a statistical significant effect on the child injury measure if the true effect size is -13%. We will not have sufficient statistical power to detect the expected effect (-20%) on the pre-term birth measure; the minimum detectable effect size with 80% power for the pre-term birth measure is -30%.

6. Recruitment Methods

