#### **2.2. Construction of Study Outcomes**

For our primary study outcome, we will assess the likelihood of experiencing injury, abuse, or neglect during early childhood. This outcome will be defined as a composite measure indicating a health care encounter or mortality associated with International Classification of Diseases (ICD) codes indicating either a major child injury or suspicion of abuse or neglect. We will identify major injury as any medical claim or mortality case that includes an ICD code associated with injury excluding superficial injuries, injuries related to medical care, and injuries stemming from allergic reactions. ICD codes indicating suspected abuse or neglect are derived from validated methods described in Schitzer et al. 2011 and Hooft et al. 2013. Data on early

childhood injury outcomes and suspected abuse or neglect will come from South Carolina all-payer hospital discharge records, Medicaid inpatient and outpatient claims and mortality records. Secondary outcomes related to injuries, suspected abuse or neglect and mortality will decompose the primary outcomes into their composite parts. In the case of multiples, we will consider a mother to experience the outcome if any of her children do and we will average the number of events in cases where the outcome is continuous (i.e. the number of injuries).

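### Protocol 5.2's nearly 100% power for child injury does not follow from its own inputs, which give about 73–81%; and the printed mean and SD cannot describe the yes/no child outcome that the SAP analyses

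*Protocol*

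**What the plan says.** Protocol 5.2 lists assumed means and SDs without the programme. Two outcomes are named as binary: "0.12 (0.32) for the binary measure for pre-term birth, 0.14 (0.34) for the binary measure of birth spacing". The third is not: "0.18 (0.30) for the measure of child injury". The expected reduction is "13% for the measure of child injury", a relative change. On size, "we need to enroll at least 6,000 women into the evaluation with a 2:1 treatment to control ratio". The section also requires at least 95% uptake in the treatment group and at most 5% of controls receiving an equally effective programme. It then states: "We will have a nearly 100% chance to detect a statistical significant effect on the child injury measure if the true effect size is -13" per cent. For birth spacing it states roughly 70% power at an 18% reduction, and for pre-term birth it concedes insufficient power.

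The test level is in Protocol 5.1: "Impact estimates with p-values less than 0.05 (two-tailed test) will be considered statistically significant".

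SAP Addendum 2, section 2.2, defines the primary child outcome as a composite of major injury or suspected abuse or neglect: "we will assess the likelihood of experiencing injury, abuse, or neglect during early childhood". It is yes/no per mother: "In the case of multiples, we will consider a mother to experience the outcome if any of her children do". The number of injuries is treated there separately, as a continuous measure.

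**The concern.** The mean, SD, effect and sample size for child injury are all printed, so the stated power can be checked directly, and it looked too high. The SD also looked out of line: the two binary outcomes have the SD that a proportion must have, and child injury does not.

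The stake is interpretation. Section 5.2 aims for 80% power or better on two of three primary outcomes, and child injury is the only one it says clears that mark. A reader who accepts nearly 100% would take a null child-injury result as strong evidence against a 13% reduction.

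**Working it through.** **Inputs.** From Protocol 5.2: mean 0.18, SD 0.30, relative effect 13%, 4,000 versus 2,000, uptake 95%, control contamination 5%. From Protocol 5.1: two-sided 0.05. Let c be the effective contrast: c = 1 with full compliance, and c = 0.95 − 0.05 = 0.90 at the stated limits.

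**Formula.** d = mean × relative effect × c; SE = SD × sqrt(1/4000 + 1/2000) = SD × 0.02739; power = Φ(d/SE − 1.96), the opposite tail being negligible.

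**Check of the method on birth spacing.** Mean 0.14, SD 0.34, effect 18%. SE = 0.00931. At c = 0.90, d = 0.02268, d/SE = 2.44 and power is 68% (70% with a two-proportion formula). The plan says roughly 70%. The method does not reproduce every figure in 5.2: for pre-term birth it gives an 80%-power minimum detectable effect of about 20–23%, against the stated 30%. So the agreement rests on birth spacing alone.

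**Child injury as printed.** SE = 0.30 × 0.02739 = 0.00822.
- c = 1: d = 0.0234, d/SE = 2.85, power 81%.
- c = 0.90: d = 0.02106, d/SE = 2.56, power 73%.

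At SD 0.30, power of 98–99% needs a reduction of about 18–20% (c = 1) or 20–22% (c = 0.90). At a 13% reduction it needs an SD of about 0.18–0.21. Reading the 13% as percentage points gives 100%, but the same reading would put birth spacing at 100% too. Taking 6,000 per arm gives 99%, which is not the design.

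**The SD.** For a 0/1 variable, SD = sqrt(p(1 − p)):
- 0.12 gives 0.325 (printed 0.32).
- 0.14 gives 0.347 (printed 0.34).
- 0.18 gives 0.384 (printed 0.30).

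A raw whole-number count with mean 0.18 has the same lower bound, because E[X²] ≥ E[X]. A rate need not. If, as an assumption, injuries over two years are Poisson with mean 0.36, the yearly rate has mean 0.18 and SD sqrt(0.36)/2 = 0.30.

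**Yes/no outcome, if 0.18 is its proportion.** With SD 0.384, SE = 0.01052.
- c = 1: d/SE = 2.22, power 60%.
- c = 0.90: d/SE = 2.00, power 52%.

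Unpooled binomial variances give 62% and 53%; a two-proportion formula with pooled null variance gives 63% and 54%. The 80%-power minimum detectable effect is 2.80 × 0.01052/(0.18c) = 16.4% (c = 1) or 18.2% (c = 0.90).

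**Yes/no outcome at other assumed rates** (13% reduction in the proportion; the range covers the variance formulas):

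| Assumed proportion | c = 1 | c = 0.90 |
|---|---|---|
| 0.10 | 35–38% | 30–32% |
| 0.18 | 60–63% | 52–54% |
| 0.25 | 78–80% | 69–72% |
| 0.35 | 94% | 88–89% |

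Under the Poisson example, the 24-month proportion with any event is 1 − exp(−0.36) = 0.30. Power is then about 67–77% if the 13% applies to the rate, or 81–89% if it applies to the proportion.

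**Analysed sample.** SAP 2.1 restricts the child analysis to index births. SAP Addendum 4, Table 3, shows 3,295 and 1,637 such mothers. At those sizes, proportion 0.18 with SD 0.384 gives 52% (c = 1) and 44% (c = 0.90).

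**The case against.** The strongest reply is that 5.2 never calls child injury binary. It uses that word for the other two outcomes and drops it for the third, and a per-year rate can have exactly this mean and SD. That stands. A reader might infer that 0.30 is an impossible value or a misprint; the documents do not show this. They show only that the pair cannot belong to a yes/no outcome or a raw count, and that 5.2 does not say what it belongs to.

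The second reply is that 5.2 describes a 2015 child-injury measure, while the SAP's composite is wider: it adds suspected abuse or neglect and draws on Medicaid claims and mortality records. That also stands. A reader might infer that the trial's power for its primary child outcome is 52–62%. That holds only if the composite's proportion is 0.18, which no section states. Nor can one say that no reading reaches nearly 100%: an assumed composite rate of 40–50% would give about 94% to over 99%.

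Third, Protocol 5.1 plans regression adjustment, which can reduce residual variance. To bring SD 0.30 down to the 0.18–0.21 needed, baseline covariates would have to explain roughly 50–64% of the variance, and 5.2 assumes nothing of the kind.

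Finally, SAP Addendum 2 refers to the published protocol paper for power. That paper may treat the composite properly and is not available here, but it does not repair the figure printed in 5.2. None of these replies yields nearly 100% from 0.18, 0.30 and 13%.

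**Conclusion.** The point holds in two parts of different strength.

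The firm part needs no assumption about the type of outcome. Protocol 5.2's inputs give about 81% power at full contrast and about 73% at its own compliance limits, not nearly 100%. At those limits no primary outcome in 5.2 reaches 80%: child injury is at 73%, birth spacing is stated at roughly 70%, and pre-term birth is conceded as underpowered.

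The second part is a gap in definition. The measure behind 0.18 (0.30) is not defined, and it cannot be the yes/no outcome in SAP 2.2. Power for that outcome therefore cannot be read from 5.2. It is about 52–62% if the proportion is 0.18, and anywhere from about 30% to 94% over assumed proportions of 0.10 to 0.35. These figures assume a 13% relative reduction, 4,000 versus 2,000, no covariate gain, and c between 0.90 and 1.

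The validity of the planned analysis is not affected. What is affected is the weight a null child result can bear.

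**What to change.** In Protocol 5.2:
- Replace the nearly 100% statement with the power the printed inputs give: about 81% at full contrast and 73% at 95% uptake and 5% contamination. If another assumption lies behind the printed figure, state it.
- Say what the 0.18 (0.30) measure is: its unit, time window and data source.
- Add a power figure for the yes/no composite of SAP 2.2 from its expected 24-month proportion p, with SD = sqrt(p(1 − p)), preferably at the index-birth sample size. Quote 52–62% only if p is 0.18.

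The 2010–2014 encounter data obtained for design (Protocol 4.7.1) can inform p. They do not include the Medicaid outpatient claims or mortality records that feed the composite, so a rate taken from them alone may be too low; show a range.

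No new participants and no change to the analysis are needed. The cost is a small amount of design work and a less favourable stated power.

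### Protocol section 5.2: the child-injury power (nearly 100%) and the pre-term minimum detectable effect (-30%) do not follow from the inputs stated beside them, which give 73–81% and about -20% to -23%

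*Protocol*

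**What the plan says.** Protocol section 5.2 plans 6,000 women at 2:1 and lists its assumptions:

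- Effects are percentage differences between arms: -20% for pre-term birth, -18% for birth spacing and -13% for child injury.
- Means (SDs) without the programme are 0.12 (0.32) for pre-term birth, 0.14 (0.34) for birth spacing and "0.18 (0.30) for the measure of child injury". The first two are called binary; the third is not.
- At least 95% of the treatment arm receives the programme, and "at most 5% of the control group that receives a home visiting program that has as much impact as NFP".

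Section 5.1 sets the test: "Impact estimates with p-values less than 0.05 (two-tailed test) will be considered statistically significant".

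From these assumptions section 5.2 reports three results:

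- Birth spacing: "roughly 70% power to detect a statistically significant effect on the birth-spacing measure if the true effect size is -18"%.
- Child injury: "nearly 100% chance to detect a statistical significant effect on the child injury measure if the true effect size is -13"%.
- Pre-term birth: "We will not have sufficient statistical power to detect the expected effect (-20%) on the pre-term birth measure", and "the minimum detectable effect size with 80% power for the pre-term birth measure is -30"%.

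The overall aim of the design is "to achieve 80% or higher chance of detecting statistically significant effects on two out of the three primary outcomes".

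**The concern.** The three outcomes have similar standardised effects on the stated inputs: 0.078 SD for injury (0.0234/0.30), 0.075 for pre-term birth (0.024/0.32) and 0.074 for birth spacing (0.0252/0.34). With a common sample size their power must therefore be similar. Yet the section reports nearly 100% for one and roughly 70% for another. For the third it gives an MDE half as large again as the expected effect.

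These figures support the 2:1 ratio and the total of 6,000; the 4,000 is the programme's own service plan. Section 4.1 says the three outcomes are of primary interest to the partners as part of the conditions for paying for the expansion. A reader who trusts the text would treat a null injury result as near-conclusive and discount a null pre-term result. On the stated inputs, the chance of missing the assumed injury effect is about 27% (100% - 73%).

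**Working it through.** **Inputs.** Section 5.2: 4,000 and 2,000 women, and the means, SDs, effects and compliance limits above. Section 5.1: two-sided 0.05. The compliance limits give a contrast c = 0.95 - 0.05 = 0.90. Results are also shown for c = 1 (no dilution).

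**Formulas.**
- SE = SD × sqrt(1/4000 + 1/2000) = SD × 0.02739
- delta = mean × relative effect × c
- power = Phi(delta/SE - 1.96)
- MDE at 80% power = 2.802 × SE / (c × mean)

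**Birth spacing first, as a check on the method.** SE = 0.34 × 0.02739 = 0.00931. At c = 0.90, delta = 0.14 × 0.18 × 0.90 = 0.0227, so power = Phi(2.436 - 1.96) = 68%. Two-proportion formulas give 69% (unpooled) and 71% (pooled). The printed figure of roughly 70% is reproduced. At c = 1 the range is 77–79%, so the printed figure fits the diluted contrast.

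**Child injury.** SE = 0.30 × 0.02739 = 0.00822.
- c = 0.90: delta = 0.18 × 0.13 × 0.90 = 0.0211; power = Phi(2.563 - 1.96) = 72.7%.
- c = 1: delta = 0.0234; power = Phi(2.848 - 1.96) = 81.3%.

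**Pre-term birth.** SE = 0.32 × 0.02739 = 0.00876.
- c = 0.90: MDE = 2.802 × 0.00876 / (0.90 × 0.12) = 22.7%.
- c = 1: MDE = 2.802 × 0.00876 / 0.12 = 20.5%.
- Two-proportion formulas: 21.8–22.3% at 0.90 and 19.7–20.2% at 1.
- Power at -20%: 69–73% at 0.90 and 78–81% at 1. A true MDE of -30% would imply Phi(2.802 × 20/30 - 1.96) = 46%.
- Power at -30%: 96% at 0.90 and 98% at 1, not 80%.

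| Figure | Printed | c = 0.90 | c = 1 |
|---|---|---|---|
| Spacing power at -18% | roughly 70% | 68–71% | 77–79% |
| Injury power at -13% | nearly 100% | 73% | 81% |
| Pre-term MDE, 80% power | -30% | -21.8% to -22.7% | -19.7% to -20.5% |

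**Could one unstated input explain both?** No.
- *Covariate adjustment.* Injury power of 99% needs an R-squared of 0.64 (0.56 undiluted). Applied to pre-term birth, that shrinks the MDE to -13.6%, further from -30%.
- *Smaller analysed sample.* An MDE of -30% needs about 3,445 women (57% of 6,000), or 2,791 (47%) undiluted. Injury power then falls to 49% and spacing to 45%, so the one figure that reproduces no longer does.
- *Other test settings.* A one-sided test with 1:1 allocation still gives at most 91.6% for injury.
- *Effect of 0.13 in SD units.* This gives 99.7% for injury. It contradicts the stated percentage scale, and the same reading makes the other two about 100%.

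**The two-of-three aim.** With powers 0.727, 0.693 and 0.683 and independent tests, P(at least two significant) = sum of pairwise products - 2 × triple product = 78.5%. The pooled formula gives 80.9%; undiluted, the range is 89–90%. If the test statistics correlate 0.3 (an assumption), it is 75% (85% undiluted). The printed figures (about 1, 0.70, and the implied 0.46) give 1 - 0.30 × 0.54 = 84%.

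**If injury is 0/1.** SD = sqrt(0.18 × 0.82) = 0.384, not 0.30. Power at -13% is then 52–54% (60–63% undiluted).

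**The case against.** The strongest defence is that each outcome had its own unstated inputs. Section 5.1 plans regression-adjusted estimates, and section 4.7.1 describes using historical data to study the predictive strength of control variables. A highly predictive model for injury, with heavy sample loss for pre-term birth, could produce both printed figures. This cannot be excluded, so the documents do not show whether the inputs or the results are at fault. But section 5.2 presents the results as following from its listed assumptions, and it lists no R-squared and no analysed sample size.

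Second, the replacement injury figure of 73% relies on an SD of 0.30 for an undefined measure. A whole-number measure with mean 0.18 cannot have an SD below 0.384, so 0.30 must be a fractional or averaged rate, an adjusted SD, or an error. This stands. The 73%, and the statement that all three powers are similar, hold only if 0.30 is right; a 0/1 measure would move injury power further from the printed figure.

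Third, the birth-spacing match is a single benchmark, and it holds only with dilution, which the section does not say it applied. That is fair, but the other two figures fail with or without dilution.

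Fourth, the stakes today are limited. The effect sizes date from May 2015 and recruitment was due to end in July 2020. The SAP refers to the published protocol for power and uses composite primary outcomes for birth and child health. This limits the finding to the text of section 5.2, which still stands in version 20.

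**Conclusion.** The concern holds. On the inputs printed in sections 5.1 and 5.2, child-injury power is 73% (81% undiluted) rather than nearly 100%. The pre-term MDE is about -22% to -23% (about -20% undiluted) rather than -30%. Taking the injury SD at face value, the three outcomes have similar power at the 0.90 contrast: 73%, 69–73% and 68–71%. The contrast drawn between injury and pre-term birth is therefore unsupported.

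This rests on a two-sample normal comparison, all 6,000 women analysed, no covariate gain, and the stated SDs. The section names no formula.

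Two lesser points need clarifying. Read per outcome, the aim of 80% on two of three conflicts with the section's own birth-spacing and pre-term statements, and no outcome reaches 80% at the 0.90 contrast. Read as the chance that at least two are significant, it is about met under independence (79–81%) and missed at a correlation of 0.3 (75%). The injury measure is also undefined.

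**What to change.** Amend section 5.2 as follows:

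1. Define the injury measure behind 0.18 (0.30) and confirm its SD. If it is 0/1, use 0.384 and report power of about 52–63%, depending on dilution and formula.
2. Then either replace the injury power and the pre-term MDE with values that follow from the stated inputs (at the 0.90 contrast, about 73% if the SD of 0.30 is confirmed, and about -22% to -23%), or state the outcome-specific covariate R-squared and analysed sample size that give the printed figures.
3. State the formula and whether the 0.90 contrast was applied.
4. Say whether the two-of-three aim is power per outcome or the chance that at least two are significant, and give the matching figure with its assumption about correlation.

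The cost is protocol wording only. Stated power becomes less favourable for child injury and more favourable for pre-term birth. No change to enrolment is proposed.
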